4.4.1.2.5 Seriousness (SAE)

No derivation or imputation was done. This information was at least listed and eventually could be summarized as collected.

4.4.1.2.6 Outcome (SAE)

No derivation or imputation was done. This information was at least listed and eventually could be summarized as collected.

4.4.1.3 Other Safety Endpoints

4.4.1.3.1 Action Taken

This information will be summarized as collected, including missing observations. No derivation or imputation will be done.

4.4.1.3.2 Causality

This information will be summarized as collected. An adverse reaction (AR) is defined as an unsolicited non-serious AE or an SAE with causality to the vaccine. Missing causality (relationship) will be handled as described in [Section 5.3.1.2](#).

4.4.1.3.3 AEs Leading to Study Discontinuation

A flag is available in the clinical database for all AEs in order to identify AEs leading to discontinuation.

In general, the items that are counted are:

- Disposition table: A subject who has, on the termination form, the reason for early termination “adverse event” is checked.
- Safety overview table: A subject who has either on the termination form, the reason for early termination “adverse event” is checked or lists an AE on an AE page (solicited, unsolicited, or SAE) that has “Reaction Leading to Termination” or “Event Leading to Termination” or “Serious Adverse Event Leading to Termination” checked that is at least Grade 1 and is within the time period indicated. Note: If the Grade is below 1, the AE will be excluded from the list of AEs leading to study discontinuation.
- System organ class (SOC)/Preferred term (PT) table: An event (solicited, unsolicited, or SAE) that has “Cause Study Termination” or “Caused Study Discontinuation” checked that is at least Grade 1 and is within the time period indicated.

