***Unsolicited AE / AR:***

An unsolicited AE is an observed AE that does not fulfill the conditions prelisted in the CRB in terms of diagnosis and/or onset window post-vaccination. For example, if headache between D0 and D7 is a solicited reaction (ie, prelisted in the protocol and CRB), then a headache starting on D7 is a solicited reaction, whereas headache starting on D8 post-vaccination is an unsolicited AE. Unsolicited AEs includes both serious (SAEs) and non-serious unsolicited AEs.

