**9.2.1.2 Safety Endpoints**

The secondary endpoints for the evaluation of safety are the description of the following in all subjects:

- Occurrence, nature (Medical Dictionary for Regulatory Activities [MedDRA] preferred term [PT]), intensity, and relationship to vaccination of any unsolicited systemic AEs reported in the 30 minutes after vaccination.
- Occurrence, time to onset, number of days of occurrence, intensity, action taken, and whether the reaction led to early termination from the study, of solicited (prelisted in the subject’s DC and CRB) injection site reactions and systemic reactions occurring up to 7 days after vaccination.

- Occurrence, nature (MedDRA PT), time to onset, duration, intensity, relationship to vaccination (for systemic AEs only), and whether the event led to early termination from the study, of unsolicited AEs up to 28 days after vaccination.
- Occurrence, nature (MedDRA PT), time to onset, seriousness criteria, relationship to vaccination, outcome, and whether the event led to early termination from the study, of SAEs (including AESIs) throughout the study.

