4.4.1.2 Unsolicited AEs

4.4.1.2.1 Occurrence

An observation will be considered an event if it has at least a verbatim term and is not a Grade 0 intensity event. Grade 0 events should be included in the listing "Unsolicited (non-serious) adverse events not included in the safety analysis."

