4.4.1.2.2 Intensity

Intensity for unsolicited AEs will be derived according to the following classification: None, Grade 1, Grade 2, Grade 3, or Missing.

If the unsolicited AE is measurable and its preferred term is part of the list of solicited reactions, then the measurement is derived based upon and following the same rule than the intensity scales defined in the protocol for that measurable injection site or systemic reaction.

Note the intensity could be considered "None" (not a reaction) in the analysis despite being considered a reaction by the investigator (eg, swelling measurement > 0 mm but < 25 mm in adults). Intensity for the other unsolicited non-serious AEs will correspond to the value reported in the electronic case report form (eCRF).

The maximum intensity corresponds to the highest intensity for a unique term.

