5.3.1.4 Intensity

For solicited reactions, missing intensities will be handled as described in [Section 4.4.1.1.1](#). For unsolicited non-serious AEs, missing intensities will remain missing and will not be imputed.

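### Read literally, SAP 4.4.1.3.3 leaves a flagged unsolicited AE or SAE with a missing grade out of the SOC/PT table of discontinuations, although SAP 4.4.1.2.1 counts it as an event

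*SAP*

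**What the plan says.** SAP 4.4.1.3.3 defines three counts of AEs leading to discontinuation.

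- **Disposition table:** subjects whose termination form gives an adverse event as the reason. There is no grade condition.
- **Safety overview:** subjects counted through the termination form, or through an AE page (solicited, unsolicited or SAE) on which the discontinuation flag is checked. The AE-page route requires an event "that is at least Grade 1 and is within the time period indicated". A Note adds: "If the Grade is below 1, the AE will be excluded from the list of AEs leading to study discontinuation".
- **SOC/PT table:** "An event (solicited, unsolicited, or SAE) that has" the discontinuation flag checked, with the same grade and time condition. The termination form plays no part here.

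For unsolicited AEs, SAP 4.4.1.2.1 states: "An observation will be considered an event if it has at least a verbatim term and is not a Grade 0 intensity event". SAP 4.4.1.2.2 gives the intensity categories as "None, Grade 1, Grade 2, Grade 3, or Missing". SAP 5.3.1.4 states: "For unsolicited non-serious AEs, missing intensities will remain missing and will not be imputed". That section has no corresponding sentence for SAEs.

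The protocol's definitions (9.2.1.1) say: "Unsolicited AEs includes both serious (SAEs) and non-serious unsolicited AEs". Protocol 9.2.1.2 includes among the secondary safety endpoints "whether the event led to early termination from the study, of SAEs (including AESIs) throughout the study", with a like item for solicited reactions and for unsolicited AEs.

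**The concern.** The two SAP rules treat a blank grade differently. The occurrence rule excludes Grade 0 and so keeps an ungraded event. The discontinuation rule requires a positive grade, which a blank cannot meet. A programmer who follows the text would therefore drop a flagged, ungraded unsolicited AE or SAE from the SOC/PT table, while the same event stays in the AE tables.

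What is at stake is a named item of the secondary safety endpoints: whether an event ended participation. The SOC/PT table is the one that shows which kinds of event did so. If an event is dropped, its subject can appear as an AE discontinuation in the disposition table and the overview with nothing against that subject in the SOC/PT table. If the termination form gives another reason, the subject is also missed by the overview, because its AE-page route has the same condition.

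Other SAP rules keep events with incomplete fields in the analysis. A missing causality counts as related (5.3.1.2), and AEs and SAEs with missing onset are included (4.4.1.2.3, 5.3.1.5). The convention is not uniform, since a blank immediate field is read as not immediate (5.3.1.1), but nothing suggests that a blank grade was meant to remove a discontinuation.

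**Working it through.** The plan gives no figure to reproduce, so the check sets the rules side by side.

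**Case considered:** an unsolicited AE or SAE with a verbatim term, inside the time period, with the discontinuation flag checked.

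| Grade | Occurs (SAP 4.4.1.2.1: not Grade 0) | In SOC/PT discontinuation table (SAP 4.4.1.3.3: Grade 1 or more) | Excluded by the Note (grade below 1) |
|---|---|---|---|
| 0 / None | no | no | yes |
| 1 | yes | yes | no |
| 2 | yes | yes | no |
| 3 | yes | yes | no |
| Missing | **yes** | **no** | **no** |

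The rules agree on every recorded grade and disagree only on Missing. There the condition leaves the event out, while the Note, taken by its words, does not exclude it. No other place in the SAP settles which prevails.

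**Can the Missing row arise?** The SAP lists Missing as an outcome (4.4.1.2.2) and leaves it unimputed for non-serious AEs (5.3.1.4). For SAEs it says nothing.

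**Solicited reactions.** Under SAP 4.4.1.1.3, occurrence is derived from maximum intensity, and a missing intensity gives a missing occurrence. An ungraded solicited reaction is therefore not counted as occurring, and the Grade 1 condition agrees with that. There is no mismatch here.

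**Effect of the change.** With the condition set to *not Grade 0* for unsolicited AEs and SAEs, the third column equals the second in all five rows.

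**Size.** Expected events lost per vaccine group = D × m, where D is the number of flagged unsolicited AEs and SAEs and m is the share without a grade. The documents give neither. Purely for scale, and as assumptions, D from 1 to 4 and m from 1% to 5% give 1 × 0.01 = 0.01 to 4 × 0.05 = 0.20 events per group.

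**The case against.** The strongest reply is that the section explains itself. The Note speaks of the list of AEs leading to discontinuation in general and removes only grades below 1. A missing grade is not below 1, so the target is Grade 0, as in the occurrence rule. This stands as evidence of intent, and it supports the fix. It does not settle the text: the Note sits in the safety overview rule, and the SOC/PT rule states only the Grade 1 condition.

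A second reply also stands in large part. Protocol 9.2.1.3.3 lists intensity among the items to record for each unsolicited AE, serious or not, so an ungraded SAE is a data gap. A reader might infer that SAE grades are absent by design, because intensity is not an SAE endpoint item, and that fatal events would routinely vanish from the table. The documents do not support that.

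Third, a reader might infer that early leavers have the least complete AE pages, so that the table is biased downward. No source in the documents says so, and several provisions work against it:

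- AEs that cause discontinuation are followed until resolved, stable or chronic unless the subject refuses contact (Protocol 5.1.4).
- Sites complete safety follow-up for subjects terminated because of an AE (5.2.11).
- SAE data are reconciled with the pharmacovigilance database (11.2).
- Queries are closed before lock (13.4.1).

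Fourth, the three counts differ by design (form, form or page, event flag) and need not agree even with complete grades. Protocol 5.2.10 also ranks adverse event first among termination reasons, so the form should usually capture these subjects. An ungraded SAE would still appear in the SAE analyses. All of this limits the harm, but it does not make the SOC/PT rule right when a grade is missing.

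**Conclusion.** The point holds for unsolicited AEs and SAEs on the literal wording. The discontinuation condition and the occurrence rule conflict for one state, a missing grade, and the result would be an incomplete count for a named secondary safety endpoint item. It is probably loose wording rather than a deliberate choice, given the Note. It does not hold for solicited reactions.

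The size cannot be computed, since the documents give neither a rate of AE-related discontinuation nor a rate of missing grade. Because such discontinuations may be few, a reader might infer that one lost event would understate a group's count by a large fraction. That takes the loss for granted, and nothing in the documents shows that even one would occur. The effect is expected to be small and is descriptive only. No safety hypothesis is tested, and the primary immunogenicity objective is not affected. If every flagged event carries a grade, no table changes.

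**What to change.** In SAP 4.4.1.3.3, in both the safety overview and the SOC/PT rules:

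- For unsolicited AEs and SAEs, replace *at least Grade 1* with *not Grade 0 (missing grade included)*, in line with 4.4.1.2.1.
- For solicited reactions, keep *at least Grade 1*, in line with 4.4.1.1.3. A blanket change would count an ungraded reaction as causing discontinuation while its occurrence is treated as missing.

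Add a sentence to SAP 5.3.1.4 saying how a missing SAE grade is handled. Optionally, list subjects whose termination form gives an adverse event as the reason but who have no event in the SOC/PT table.

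The cost is a few words in the SAP and one programming condition, plus a short listing if wanted. No new data are needed.

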4.4.1.3.4 AEs of Special Interest (AESIs)

AESIs will be collected throughout the study (from the inclusion until the D180 safety follow-up contact after vaccination). AESIs are to be reported as SAEs. Each AESI will be retrieved using the following (as shown in [Table 4.4](#)):

Table 4.4: AESI PTs

AESI	PT
Guillain-Barré Syndrome (GBS)	Chronic inflammatory demyelinating polyradiculoneuropathy Demyelinating polyneuropathy Guillain-Barré syndrome Miller Fisher syndrome
Bell’s Palsy	Facial paralysis Facial paresis
Encephalitis/Myelitis (including Transverse Myelitis)	Myelitis Myelitis transverse Encephalitis is using the narrow Standardized MedDRA Query (SMQ) term “Noninfectious encephalitis” (Medical Dictionary for Regulatory Activities [MedDRA 22.1])
Optic Neuritis	Optic neuritis Optic neuropathy
Brachial Neuritis	Radiculitis brachial Brachial plexopathy Neuralgic amyotrophy

4.4.1.3.5 Subjects with at-risk condition

At-risk subjects with stable chronic illness are eligible for inclusion unless they could interfere with trial conduct or completion. Subjects with specific chronic diseases such as chronic respiratory, heart, renal, metabolic or hematological disorders will be identified by medical review through reported Medical History.

4.4.2 Immunogenicity

4.4.2.1 Computed Values for Analysis

In order to appropriately manage extreme values (< lower limit of quantification [LLOQ] and ≥ upper limit of quantification [ULOQ]) for analysis purposes, the following computational rule is applied to the values provided in the clinical database for each BL drawn:

- If a value is < LLOQ, then use the computed value LLOQ/2
- If a value is ≥ LLOQ and < ULOQ (or ≤ ULOQ), then use the value
- If a value is ≥ ULOQ (or > ULOQ), then use the computed value ULOQ

Duplicate records (per subject, antigen, and method) were recorded for HAI titration. A geometric mean of duplicate was applied in order to obtain a unique value for the statistical analysis. Unique records were recorded for SN and enzyme-linked lectin assay (ELLA) titration.

4.4.2.2 Fold-rise

The derived endpoint fold-rise is driven by both baseline and post-baseline computed values which are computed as described in [Section 4.4.2.1](#). The computed value for fold-rise is:

- Computed value = Post-vaccination computed value / Baseline computed value.

For HAI assay, if the computed value is ≥ 4 -fold rise, then the derived 4-fold rise indicator will be “Yes” for that test, otherwise the corresponding indicators will be “No”.

For SN and ELLA assays, if the computed value is ≥ 2 -fold rise or 4-fold rise, then the derived corresponding 2-fold rise or 4-fold rise indicator will be “Yes” for that test, otherwise the corresponding indicators will be “No”.

Note: If baseline or post-baseline is missing, then the fold-rise is missing.

4.4.2.3 Seroconversion

Seroconversion is defined for HAI assay as either

- A computed value < 10 [1/dil] at D0 and post-injection computed value ≥ 40 [1/dil] at D28, or
- A computed value ≥ 10 [1/dil] at D0 and a ≥ 4 -fold rise in computed titer values [1/dil] at D28 as described in [Section 4.4.2.1](#).

4.4.3 Efficacy

Not applicable.

4.4.4 Derived Other Variables

4.4.4.1 Age for Demographics

The age of a subject in the study was the calendar age in years at the time of inclusion. The age calendar was the age computed automatically in the eCRF, and presented as an integer.

4.4.4.2 Duration of the Study

The duration of the study is computed in days as follows:

- Maximum (Visit dates, Termination date, safety follow-up date) – minimum (V01 date) + 1

The duration of the active phase of the study is computed in days as follows:

- Maximum (latest date of V02, latest date of termination during the active phase) – minimum (V01 date) + 1,

The duration of the D180 safety follow-up phase of the study is computed in days as follows:

- Maximum (date of D180 safety follow-up) – minimum (V02 dates, termination dates during the active phase) + 1.

4.4.4.3 Subject Duration

The duration of a subject participation in the trial, including the D180 safety follow-up, is computed as follows:

- Maximum (visit dates, termination date, safety follow-up date) – V01 date + 1.

The duration of a subject in the active phase of the trial is computed as follows:

- Maximum (V02 dates, termination date) – V01 date + 1.

4.4.4.4 Time Interval

The time interval between 2 visits/vaccinations/blood samples is computed as follows:

Later date – earlier date.

4.4.4.5 Influenza Vaccination during the 3 Past Influenza Seasons (2016-2017, 2017-2018, and since 01SEP2018)

This information will be used as collected. No derivation or imputation will be done.

5 Statistical Methods and Determination of Sample Size

The statistical analyses will be performed under the responsibility of the Sponsor’s Biostatistics platform using SAS® Version 9.4 software or later.

The results of the statistical analysis will be available in the final clinical study report (CSR).

For descriptive purposes, the following statistics will be presented:

Table 5.1: Descriptive statistics produced

Baseline characteristics and follow-up description	Categorical data	Number of subjects. Percentage of subjects.
	Continuous data	Mean, standard deviation, quartiles, minimum, and maximum.
Clinical safety results	Categorical data	Solicited: Number and percentage (95% confidence intervals [CIs]) of subjects. Unsolicited: Number and percentage (95% CIs) of subjects, and number of events.
Immunogenicity results	Categorical data (seroconversion, cutoff)	Number and percentage (95% CIs) of subjects.
	Continuous data (titer / data)	Log10: Mean and standard deviation. Anti-Log10 (work on Log10 distribution, and anti-Log10 applied): Geometric mean, 95% CI of the geometric mean, quartiles, minimum, and maximum. Graphical representation by Reverse Cumulative Distribution Curve (RCDC).

The CI for the single proportion will be calculated using the exact binomial method (Clopper-Pearson method, quoted by Newcombe (1), ie, using the inverse of the beta integral with SAS®).

For immunogenicity results, assuming that Log10 transformation of the titers / data follows a normal distribution, at first, the mean and the 95% CI will be calculated on Log10 (titers / data) using the usual calculation for normal distribution (using Student's t distribution with n-1 degree of freedom), then antilog transformations will be applied to the results of calculations, in order to provide GMs and their 95% CI.

5.1 Statistical Methods

For the purposes of the statistical methods section, the 4 virus strains in the QIV-HD trial groups and the QIV-SD trial groups will be labeled as follows:

- A/(H1N1)-like strain A/H1N1
- A/(H3N2)-like strain A/H3N2
- B/(Victoria Lineage)-like strain B1
- B/(Yamagata Lineage)-like strain B2

5.1.1 Hypotheses and Statistical Methods for Primary Objective

5.1.1.1 Superiority of QIV-HD to QIV-SD

5.1.1.1.1 Hypotheses

A superiority approach will be used to compare post-vaccination GMTs between QIV-HD and QIV-SD groups for each strain and in each age group using a 1-sided test with Type I error rate of 0.025 following the individual hypotheses:

$$H_0^s : \frac{GMT_{QIV-HD}^s}{GMT_{QIV-SD}^s} \leq 1 \Leftrightarrow \log_{10}(GMT_{QIV-HD}^s) - \log_{10}(GMT_{QIV-SD}^s) \leq 0$$

$$H_A^s : \frac{GMT_{QIV-HD}^s}{GMT_{QIV-SD}^s} > 1 \Leftrightarrow \log_{10}(GMT_{QIV-HD}^s) - \log_{10}(GMT_{QIV-SD}^s) > 0$$

where

s: strain

If superiority is demonstrated for post-vaccination GMTs for the 4 strains within a same age group, then the immunogenicity of QIV-HD will be considered as superior to QIV-SD in the corresponding age group.

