5.1.1.1.2 Statistical Methods

The statistical methodology will be based on the use of the lower bound of the 2-sided 95% CIs of the ratio of post-vaccination GMTs between the QIV-HD and QIV-SD groups. The CIs will be calculated by normal approximation of log-transformed titers for GMTs.

The superiority objective will be achieved if it is demonstrated for the 4 strains in each age groups. Analyses will be performed for both the Full Analysis Set (FAS) and the Per-protocol Analysis Set (PPAS), but the conclusion will be made from PPAS results.

A sensitivity analysis will be performed with adjustment on the pre-vaccination HAI titers. Superiority objective will be analyzed on the PPAS and FAS through an analysis of covariance (ANCOVA) model, using the HAI titers at D0 as a covariate for adjustment, in order to account for the variability linked to the baseline HAI titer and to provide a "change from baseline" analysis.

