5.5 Determination of Sample Size and Power Calculation

A total of approximately 1540 adults 60 years of age and older (770 adults 60 to 64 years of age and 770 adults 65 years of age and older) will be enrolled. This sample size is determined per simulations based on an overall power of 90% for demonstrating the primary objective. The thresholds for superiority are defined as 1 for GMTs. No alpha adjustment is needed. Other assumptions are listed as follows:

- Allocation ratio: 1:1 (QIV-HD versus QIV-SD)
- GMT ratio: 1.5 for all strains
- Standard deviations of log₁₀-transformed titers in QIV-SD group of 0.6 for 2 strains and 0.5 for the other 2 strains
- Attrition rate: 5% in FAS

It should be noted that the power per strain is 97.7% when the standard deviation is 0.6 and 99.7% when the standard deviation is 0.5.

An arbitrary number of subjects, ie, at least 50% of subjects in each age group and each vaccine group will be randomly assigned to the observational subset of subjects for SN testing and at least 50 subjects in each age group and each vaccine group for NA testing as shown in [Table 5.2](#).

Table 5.2: Random assignment of subjects to observational subsets

Vaccine/Assay	Number of subjects 60 to 64 years of age	Number of subjects 65 years of age and older	Total
QIV-HD Group/SN	≥ 193	≥ 193	≥ 386
QIV-SD Group/SN	≥ 193	≥ 193	≥ 386
QIV-HD Group/NA	≥ 50	≥ 50	≥ 100
QIV-SD Group/NA	≥ 50	≥ 50	≥ 100

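### Two success rules coexist, and the no-adjustment statement covers the both-age-groups objective and each age-group claim singly, but not the two stand-alone claims together (up to 4.94% one-sided)

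*SAP*

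**What the plan says.** SAP 5.1.1.1.1 sets the tests "for each strain and in each age group using a 1-sided test with Type I error rate of 0.025". It then gives a conclusion for a single age group: when all four strains succeed there, "then the immunogenicity of QIV-HD will be considered as superior to QIV-SD in the corresponding age group". No condition is placed on the other age group. The Statistical Methods part of the protocol synopsis carries the same rule.

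SAP 5.1.1.1.2 gives a different rule: "The superiority objective will be achieved if it is demonstrated for the 4 strains in each age groups". This agrees with the primary objective (protocol 2.1, SAP 2.1), which joins the two age groups with 'and'.

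SAP 5.5 says of the sample size: "This sample size is determined per simulations based on an overall power of 90% for demonstrating the primary objective". Shortly afterwards it says "No alpha adjustment is needed". The same statements stand in protocol 12.5 and in the synopsis under Calculation of Sample Size. None of these places says which success rule the no-adjustment statement refers to. Neither document gives a testing order, a gatekeeping step or a split of alpha between the age groups.

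**The concern.** The two rules give different answers when one age group succeeds on all four strains and the other does not. By SAP 5.1.1.1.2 the primary objective has failed. By SAP 5.1.1.1.1 superiority is established in the group that succeeded.

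A one-group result would matter. Protocol 1.4 gives the groups separate purposes: the 60–64 group is there to extend the age indication, and the group aged 65 and over is there because the high-dose vaccine has not yet been compared with a standard-dose quadrivalent vaccine licensed in Europe. Success in either group alone would be of interest for labelling and publication.

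Allowing either group to be claimed is a union of two tests, each at the full 0.025. The plan offers no argument that this needs no adjustment, and the status of such a claim would be open to debate after the results are known.

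**Working it through.** **Inputs** (SAP 5.5 and 5.1.1.1.1)
- 385 randomised per arm per age group; 5% attrition leaves about 365.
- "GMT ratio: 1.5 for all strains", so the log10 difference is 0.1761.
- Standard deviations of log10 "titers in QIV-SD group of 0.6 for 2 strains and 0.5 for the other 2 strains". I assume the same values in the high-dose arm.
- One-sided 0.025 per test.

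**Step 1: reproduce the plan's power.** Power per strain = Φ(0.1761 / (SD × √(2/365)) − 1.96).
- SD 0.6: Φ(3.965 − 1.960) = 97.75% (plan: 97.7%).
- SD 0.5: Φ(4.758 − 1.960) = 99.74% (plan: 99.7%).
- One age group, four strains treated as independent: 0.9775² × 0.9974² = 95.1%.
- Both age groups: 0.9506² = 90.4%. From the plan's rounded figures: (0.977² × 0.997²)² = 90.0%.

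The stated 90% is therefore the power of the both-groups rule. A single age group has about 95%.

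**Step 2: error under each rule**
- One age group, all four strains required: an intersection-union test, so at most 2.5%.
- Both groups required (all eight tests): at most 2.5%.
- Either group may be claimed: the groups contain different subjects, so with a null strain in each the chance of at least one false claim is at most 1 − (1 − 0.025)² = 4.94%.

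**Step 3: how close to the ceiling?** Simulation with 1,000,000 runs per scenario, independent age groups, and a common correlation between strains:

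| Strain correlation | One null strain per group, other three at design effect | No strain has an advantage |
|---|---|---|
| 0 | 4.81% | about 0% |
| 0.3 | 4.90% | 0.02% |
| 0.5 | 4.94% | 0.15% |
| 0.8 | 4.92% | 1.03% |
| 1 | 4.97% | 4.94% |

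The 4.97% exceeds the bound only by simulation noise. In the one-null-strain scenario the both-groups rule had an error of about 0.06%.

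**Step 4: how often do the rules disagree?** Under the planning assumptions, P(exactly one group succeeds) = 2 × 0.9506 × 0.0494 = 9.4% with independent strains. From the simulation, P(at least one) − P(both) is:
- correlation 0.3: 0.9978 − 0.9078 = 9.0%
- correlation 0.5: 0.9981 − 0.9138 = 8.4%
- correlation 0.8: 0.9987 − 0.9297 = 6.9%

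**Step 5: cost of Hochberg across the two groups.** Take each group's p-value as the largest of its four strain p-values.
- If both are at most 0.025, both groups are claimed, so the power of the both-groups objective stays at 90.4%.
- If only one succeeds, it is claimed only at one-sided 0.0125. Age-group power at that level is 0.9576² × 0.9941² = 90.6%.
- Chance of losing a single-group claim: 2 × 0.0494 × (0.9506 − 0.9061) = 0.44 percentage points.
- Worst-case error, null strain in both groups: [2(0.0125) − 0.0125²] + 0.0125² = 2.5%.

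**The case against.** The strongest reply is that the plan promises no family-wise rate. Its 0.025 is a rate per test, and because all four strains must succeed, each age-group claim keeps to it. This stands. A reader might infer that each stand-alone claim carries a 4.9% error, or that a one-group conclusion falls outside the stated 2.5%. The documents support neither: 4.94% is the chance of at least one false claim across the two.

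A second reply is that the no-adjustment sentence closely follows the sentence on power for the primary objective and, read in that place, is correct. This is a fair reading, so the sentence should not be called simply wrong. But nothing ties it to that objective, and SAP 5.1.1.1.1 words the single-group result as a conclusion, not as a step towards the joint rule.

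A third reply is that the age groups are separate strata with separate purposes, so whether to control error across them is a judgement. That is so. The SAP does not make that argument, however: it places both groups under one primary objective with one joint power figure. If the sponsor holds that view, it should be written down and squared with SAP 5.1.1.1.2.

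Finally, the 9% could be mistaken for an error rate. It is not. It is computed with a true ratio of 1.5 for every strain in both groups, so every single-group claim it counts would be correct. It shows only how often the labelling question would arise.

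**Conclusion.** The point holds as a gap in the decision rule. The no-adjustment statement is justified for the both-groups objective and for each age-group claim singly. It is not justified across the two stand-alone claims that SAP 5.1.1.1.1 permits, where the chance of at least one false claim is at most 4.94% one-sided.

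That ceiling assumes independent age groups and a null strain in each. It is nearly reached when the remaining strains have the design effect. When no strain has an advantage it is about 1% or less at strain correlations up to 0.8.

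The disagreement between the rules is not remote: about 9% with independent strains and about 7–9% at correlations of 0.3–0.8, given the plan's effect size, standard deviations and attrition. The joint primary objective itself is sound. What needs settling is the status of a one-group success.

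**What to change.** 1. In SAP 5.1.1.1.1 and 5.1.1.1.2, name success on four strains in both age groups as the primary success rule.
2. In SAP 5.5, limit the no-adjustment statement to that rule.
3. Before unblinding, state how a one-group success is handled, by one of these routes:
   - **Supportive only.** No new procedure, but a lone success (about 7–9% under the planning assumptions) is not confirmatory.
   - **Fixed sequence of age groups, each at 0.025.** Family-wise error is at most 2.5%. The second group cannot be claimed if the first fails; with independent strains that loses a claim with probability 0.0494 × 0.9506 = 4.7%.
   - **Hochberg.** If only one group succeeds, claim it only when all four strains meet one-sided 0.0125 (lower bound of the two-sided 97.5% interval above 1). This costs at most about a 0.4 percentage-point chance of losing a single-group claim.

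Any of these is acceptable; Hochberg is one option, not a requirement. Power for the both-groups objective stays at about 90% under all three.

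Make matching edits in the protocol: the synopsis (Statistical Methods and Calculation of Sample Size) and section 12.5. The body of protocol 12.1.1.1.1 was not in the text available for this review and should be checked for the same wording. The work is a few sentences in each document, with no change to sample size or conduct.
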